# 1.2.1.2.1.9. Study B7461016

Study B7461016 was a Phase 1, randomized, single-dose, open-label, 4-period, 4-treatment,4-sequence, crossover study balanced for first order residual effect in 20 healthy adult volunteer subjects employing administration of the Phase 2 clinical lorlatinib tablets (Reference:  $4 \times 25$ -mg tablets) and the 3 proposed commercial lorlatinib tablet strengths (Test formulations:  $4 \times 25$ -mg tablets,  $2 \times 50$ -mg tablets,  $1 \times 100$ -mg tablet) under fasted conditions.

A total of 20 subjects were screened with 5 subjects assigned to each of the 4 sequences. All subjects completed the study.

Bioequivalence was demonstrated for each of the Test formulations (lorlatinib commercial  $4 \times 25$ -mg tablets, commercial  $2 \times 50$ -mg tablets and commercial  $1 \times 100$ -mg tablet) versus the Reference (lorlatinib clinical  $4 \times 25$ -mg tablets) in healthy volunteers under fasted conditions. The 90% CIs of ratios of adjusted geometric means (Test/Reference) fell wholly within the bioequivalence limits (80%-125%) for AUCinf and Cmax for all 3 treatment comparisons. All treatments were safe and well-tolerated in healthy volunteers evaluated in this study under fasted conditions.

Additional information for this compound may be found in the single reference safety document (SRSD), which for this study is the investigator's brochure.

### 1.2.2. Study Rationale

Lorlatinib elimination occurs primarily through liver metabolism as noted in both in vitro and clinical assessments. CYP3A is one of the primary metabolizing enzymes involved in the metabolism of lorlatinib. Furthermore lorlatinib demonstrates both inhibitory and inducing effects on CYP3A. With continuous once daily dosing, the net effect of lorlatinib on its own metabolizing enzyme, CYP3A, is auto-induction at the majority of clinically tested dose levels including the RP2D of 100 mg QD. The change in liver function may potentially change the inhibitory and/or inducing potential of the liver metabolizing enzymes. Thus the effect of lorlatinib on its own metabolism in patients with hepatic impairment may differ from patients with normal hepatic function. As there may be a need to use lorlatinib to treat cancer patients who also have impaired liver function, it is important to determine the effects of hepatic impairment on the pharmacokinetics and safety of lorlatinib and also, if possible, determine whether dose modification would be necessary in these patients.

The current study is designed to primarily evaluate the effect of hepatic impairment on the steady state pharmacokinetics and safety of lorlatinib in advanced cancer patients, and if possible, provide dosing recommendations for patients with impaired liver function.

Since lorlatinib induces its own metabolism at the relevant dose levels, multiple dose lorlatinib exposures may not be predicted from single dose PK data. The potential effect of the liver dysfunction on the inhibitory and inducing effects of lorlatinib can only be seen after multiple administrations at steady-state. Hence the current hepatic impairment study will be conducted following multiple dosing with lorlatinib. Since the administration of multiple doses to healthy volunteers is precluded, the current study will be conducted in patients with solid tumors who do not have other treatment options.

The preliminary PK data from the lorlatinib clinical study B7461001 in ALK-positive NSCLC pateints showed that systemic exposure of lorlatinib is comparable in patients with mild hepatic impairment and patients with normal hepatic impairment. These results suggested a therapeutic dose of 100 mg QD (same as the current RP2D of 100 mg QD) may be tolerable in patients with mild hepatic impairment. Theoretically, liver enzyme activity may be affected by worsening liver dysfunction, thus, use of a lower starting dose of lorlatinib for patients with moderate hepatic impairment may be necessary before an appropriate dose level in this population of patients is identified. An initial dose of 50 mg QD of lorlatinib will be administered to patients with moderately impaired liver function, while, patients with mildly impaired liver function will start at the proposed fulldose of 100 mg QD of lorlatinib. Dosage modifications may be applied during the study based on the tolerability of the starting doses. Dosing patients with severe hepatic impairment will not be initiated until initial PK and safety information is available for patients with moderate hepatic impairment.

This study will permit enrolment of patients with cancer who may or may not harbor ALK or ROS1 mutations. Patients who do not harbor ALK or ROS1 mutations may not derive clinical benefit with lorlatinib, and should not have a high expectation of therapeutic benefit from lorlatinib treatment.

Providing these biospecimens is a required study activity for study sites and patients, unless prohibited by local regulations or ethics committee (EC) decision.

# 2. STUDY OBJECTIVES AND ENDPOINTS

Primary Objective(s):	Primary Endpoint(s):				
• To evaluate the effect of hepatic impairment on the steady state pharmacokinetics of lorlatinib in advanced cancer patients.	• Plasma PK parameters of lorlatinib at steady state: $AUC_{24}$ and $C_{max}$ .				
Secondary Objective(s):	Secondary Endpoint(s):				

 
To evaluate the effect of hepatic impairment on the safety of lorlatinib in advanced cancer patients.
 
To evaluate the antitumor activity of lorlatinib in advanced cancer patients.
 
	
 
Type, incidence, severity, seriousness, and relationship to study medications of adverse events (AE) and any laboratory abnormalities.
 
Objective response rate (ORR).
 
Duration of response (DR).
 
Plasma PK parameters of lorlatinib, if possible:         
 
After single dose: AUC24, Cmax, AUClast, Tmax, Clast, and Tlast.
 
At steady-state: Cmin, AUClast, Tmax, Tlast, and CL/F.
 
 
 
Plasma PK parameters for metabolite(s) if possible: After single dose and at steady-state: AUC24, AUClast, Cmax, Clast, Tmax, Tlast, MRAUC24, MRAUClast, and MRCmax.
 
				
CCI					

### **3. STUDY DESIGN**

#### 3.1. Study Overview

This will be a Phase 1, open-label, multi-center, multiple-dose, non-randomized, Phase 1 clinical trial of lorlatinib in advanced cancer patients with varying degrees of hepatic impairment and necessary age-, weight-, and gender-matched prospect normal hepatic function patients.

Patients in the study will be assigned to different groups according to their liver function. The criteria for stratification of patients based on their liver function (according to National Cancer Institute (NCI) guidance,

https://ctep.cancer.gov/protocolDevelopment/docs/CTEP\_Organ\_Dysfunction\_Protocol\_Te mplate.docx) are listed below:

Group	Groups A1	Groups A1 Group B		Group D	
	and A2				
Hepatic	Normal	Mild impairment	Moderate	Severe	
Function		1	impairment	impairment	
Total	$\leq$ ULN (Upper	B1:≤ULN	>1.5 x – 3 x	>3 x ULN	
Bilirubin	Limit of	B2: >1.0 x – 1.5 x ULN	ULN		
	Normal)				
AST	$\leq$ ULN	B1:>ULN	Any	Any	
(SGOT)		B2: Any			

- Patients must fulfill both total bilirubin and AST (serum glutamic oxaloacetic transaminase [SGOT]) criteria to be included in a group.
- No distinction will be made between liver dysfunction due to metastases or liver dysfunction due to other causes.
- All liver function tests for stratification must be completed within 24 hours prior to the start of treatment.
- Group B (Mild hepatic impairment): for the purpose of this study, the "mild" liver dysfunction may be defined according to either of two criteria (Groups B1 and B2), so that patients in Group B may come from either of these groups. Patients in Group B1 and B2 are thus considered to have comparable liver dysfunction and will be combined for dose level allocation and all analysis.
- Patients whose degree of hepatic dysfunction changes (becomes worse or better) between screening and initiation of protocol therapy may be re-assigned to a different hepatic dysfunction group. This change should be discussed with the Sponsor and properly documented. Patient stratification will only be done prior to initiation of the study treatment. Patients will not be re-assigned to a different hepatic dysfunction group once treatment with lorlatinib has been started.
- Groups A1 and A2 (Normal): patients with normal liver function will be included in this study as matching control patients (Group A1 for Group B and Group A2 for Group C). If the dose for moderate hepatic impairment group (Group C) is selected to be the recommended clinical dose of 100 mg QD, the control group A2 will not be needed to be enrolled. There will be no control group designated to match severe group. However, if a decision has been made to use the same dose for severe and moderate patients, the half of the control Group A2 will be matching Group C and half will be matching Group D.

Child-Pugh scores (criteria listed in Appendix 3) will be calculated and recorded as part of the liver function testing prior to the start of the first lorlatinib dose, but will not be used to stratify patients into treatment groups.

The enrollment of approximately 76 advanced cancer patients is anticipated in this study in order to have 8 PK-evaluable patients in each of Groups A1, A2, B and C, and 6 PK-evaluable patients in Group D for final statistical analysis. Evaluable patients are those who complete the planned PK sample collection on Cycle 2 Day 1 and have no lorlatinib dose modification until completion of Cycle 2 Day 1 PK evaluation. Patients who are not evaluable for PK will be replaced.

Each patient will be treated with repeated oral once daily doses of lorlatinib in 21-day cycles until disease progression, patient refusal, or unacceptable toxicity occurs.

The planned dosing schedule for each treatment group is as follows (Table 4):

	Group B	Group C	Group D	Group A1	Group A2
Hepatic Function	Mild	Moderate	Severe	Normal	Normal
Starting Lorlatinib Dose	100 mg QD	50 mg QD or otherwise determined in the first stage	determined based on preliminary safety and PK data	100 mg QD	the same dose as Group C at the second stage
Lorlatinib Dose After PK Assessment	100 mg QD	50 mg QD or otherwise determined in the first stage	determined based on preliminary safety and PK data	100 mg QD	100 mg QD

Table 4.Lorlatinib Dosing Schedule

The dose schedule may be modified as necessary for individual patients according to tolerability (see Table 6 for detailed dose modification strategy).

For Group C, a two-stage enrollment will be applied.

• In the first stage, 3 PK-evaluable patients will be enrolled to receive the starting dose of 50 mg QD lorlatinib. On completion of PK sample collection through Cycle 2 Day 1 from these 3 patients, PK analysis will be performed. Upon review of the PK and tolerability of these 3 patients, a decision on dose schedule for remaining patients in the second stage will be made.

- In the second stage:
  - If it is decided to keep the planned dosing schedule (50 mg QD) for patients in Group C with moderately impaired liver function, 5 additional patients will be enrolled to have a total of 8 PK evaluable patients.
  - If a different dosing schedule is proposed for the remaining patients in Group C based on safety and PK in the first 3 subjects, then more patients will be enrolled to this group to have 8 PK evaluable patients and receive the proposed dosing schedule. The control patients in Group A2 should receive the same lorlatinib dose as proposed for the second stage in Group C until completion of PK assessment on Cycle 2 Day 1 and then switch to 100 mg QD beyond Cycle 2 Day 1. At the new dose level, the first 3 patients should be dosed one at a time with at least one week apart until some safety information at this dose level is obtained.

The enrollment for patients with severe hepatic impairment (Group D) will only be started when the dose for patients in the second stage of Group C has been determined and has been tolerated in at least one patient. The initial lorlatinib dose for Group D might be the same as the second stage Group C dose or otherwise determined by sponsor based on available preliminary safety and PK data at that time. The dosing regimen for Group D will be communicated to sites. Patients in Group D will not be matched by any control group. Initially (the first 3 patients), the patient should be dose one by one with at least 1 week apart until some safety information is obtained at the dose level.

Patients in Groups A1 (Normal hepatic function) and B (Mild hepatic impairment) will receive a starting lorlatinib dose of 100 mg ( $4 \times 25$ -mg tablets) QD. The first 3 patients in in Group C (Moderate hepatic impairment) will receive a starting lorlatinib dose of 50 mg ( $2 \times 25$ -mg tablets) QD. Patients in control Group A2 (Normal hepatic function) will receive the same starting lorlatinib dose as stage 2 of Group C, which could be 50 mg ( $2 \times 25$ -mg tablets) QD or as otherwise determined during the second stage of Group C, and switch to 100 mg ( $4 \times 25$ -mg tablets) QD after completion of PK assessment on Cycle 2 Day 1.

Enrollment into control Group A2 will only be started after the first stage for Group C has been completed and a decision on dose schedule for the stage 2 subjects in Group C has been made. Patients in control group should match patients in the respective hepatic impaired group by the following criteria:

- The mean body weight in control group will be within ±20 kg of the mean body weight of the patients in respective hepatic impaired group.
- The mean age in control group will be within ±10 years the mean age of the patients in respective hepatic impaired group.
- The gender ratio in control group will be similar (±2 patients per gender) to those in respective hepatic impaired group.

Once all the patients complete their planned PK collection, data collection for the primary objective of the study will be accomplished. After data collection for the primary objective has been completed, the sponsor could generate a study report including all PK data and other data, as defined in the Sponsor-maintained statistical analysis plan. In this case, a supplement study reported will then be generated when all patients completed the study.

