## 9.1. Analysis Sets

1. Safety analysis set:

The safety analysis set includes all enrolled patients who receive at least one dose of lorlatinib.

2. Full analysis set:

The full analysis set includes all enrolled patients.

3. PK analysis sets:

The PK concentration population is defined as all enrolled patients who are treated and have at least 1 analyte concentration.

The PK parameter analysis population is defined as all enrolled patients treated who have sufficient information to estimate at least 1 of the PK parameters of interest.

The PK evaluable analysis population is defined as all patients in the PK parameter analysis population who have (1) completed Cycle 2 Day 1 PK collection; (2) received lorlatinib dose on Cycle 2 day 1; (3) received at least 80% of total dose within 14 days prior to Cycle 2 Day 1; (4) no dose reduction in the first cycle.

4. Response Evaluable set – includes all patients in the safety analysis population who have an adequate baseline tumor assessment.

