- In the first stage, 3 PK-evaluable patients will be enrolled to receive the starting dose of 50 mg QD lorlatinib. On completion of PK sample collection through Cycle 2 Day 1 from these 3 patients, PK analysis will be performed. Upon review of the PK and tolerability of these 3 patients, a decision on dose schedule for remaining patients in the second stage will be made.
- *In the second stage:*
 - If it is decided to keep the planned dosing schedule (50 mg QD) for patients in Group C with moderately impaired liver function, 5 additional patients will be enrolled to have a total of 8 PK evaluable patients.

• If a different dosing schedule is proposed for the remaining patients in Group C based on safety and PK in the first 3 subjects, then more patients will be enrolled to this group to have 8 PK evaluable patients and receive the proposed dosing schedule. The control patients in Group A2 should receive the same lorlatinib dose as proposed for the second stage in Group C until completion of PK assessment on Cycle 2 Day 1 and then switch to 100 mg QD beyond Cycle 2 Day 1. At the new dose level, the first 3 patients should be dosed one at a time with at least one week apart until some safety information at this dose level is obtained.

The enrollment for patients with severe hepatic impairment (Group D) will only be started when the dose for patients in the second stage of Group C has been determined and has been tolerated in at least one patient. The initial lorlatinib dose for Group D might be the same as the second stage Group C dose or otherwise determined by sponsor based on available preliminary safety and PK data at that time. The dosing regimen for Group D will be communicated to sites. Patients in Group D will not be matched by any control group. Initially (the first 3 patients), the patients should be dosed one by one with at least 1 week apart until some safety information is obtained at the dose level.

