3.4.2.3. PK evaluable Analysis set

The PK evaluable analysis set is defined as all patients in the PK parameter analysis population who have (1) completed Cycle 2 Day 1 PK collection; (2) received lorlatinib dose on Cycle 2 day 1; (3) received at least 80% of total dose within 14 days prior to Cycle 2 Day 1; (4) no dose reduction in the first cycle.

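### The Group C stage-2 dose decision rests on the tolerability of 3 PK-evaluable patients, a set that by definition excludes anyone whose dose was reduced or stopped in Cycle 1

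*Protocol*

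**What the plan says.** Group C is enrolled in two stages. Stage 1 takes 3 PK-evaluable patients at 50 mg QD. Protocol 3.1 then gives the basis for the stage-2 dose: "Upon review of the PK and tolerability of these 3 patients, a decision on dose schedule" for the remaining patients is made. SAP 2.2 has the same rule: "Upon review of the PK and tolerability of these 3 patients, a decision on dose schedule for remaining patients". Where a different dose is chosen, both documents describe the choice as "based on safety and PK in the first 3 subjects".

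Protocol 3.1 defines evaluable patients as those who complete the Cycle 2 Day 1 PK sampling and "have no lorlatinib dose modification until completion of Cycle 2 Day 1 PK evaluation. Patients who are not evaluable for PK will be replaced". Protocol 9.1 words the PK evaluable set differently. Besides completed Cycle 2 Day 1 sampling and a dose that day, it requires that the patient "received at least 80% of total dose within 14 days prior to Cycle 2 Day 1; (4) no dose reduction in the first cycle". SAP 3.4.2.3 repeats those conditions.

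For starting doses, Protocol 3.1 says: "The first 3 patients in in Group C (Moderate hepatic impairment) will receive a starting lorlatinib dose of 50 mg". SAP 6 times an interim PK and safety analysis by the third PK-evaluable patient in group C1 and uses it to set the regimen for groups C2 and D. It does not say whose safety data enter that analysis.

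**The concern.** PK evaluability is a sensible filter for steady-state exposure, because a patient whose dose was cut does not give a clean 50 mg profile. It is the wrong filter for tolerability. A patient who could not stay on 50 mg is the most informative one for that question, and the filter removes and replaces that patient.

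Table 6 of the Protocol makes this concrete. For Grade 2 or 3 CNS effects, and for other reactions of Grade 3 or above, it recommends holding lorlatinib and resuming one level lower. For Grade 4 CNS effects it recommends permanent discontinuation. A patient managed that way in Cycle 1 falls outside the named set.

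The decision can keep, lower or raise the dose for the rest of Group C. Protocol 3.1 expressly foresees 100 mg QD. Through SAP 6 the same look also informs the dose for severely impaired patients. Read literally, the tolerability evidence for that step is selected on having tolerated the dose.

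**Working it through.** **1. Who can be in the named set.** The two definitions of evaluable, side by side:

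| Cycle 1 event at 50 mg | Protocol 3.1 | Protocol 9.1 / SAP 3.4.2.3 |
|---|---|---|
| Dose reduction | excluded | excluded |
| Stop before Cycle 2 Day 1 | excluded | excluded |
| Short interruption, same dose resumed | excluded if counted as a dose modification | allowed if at least 80% of the dose was taken in the prior 14 days |
| Toxicity with no dose change | included | included |

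The 80% rule: 0.80 × 14 = 11.2, so 12 of 14 doses are needed. At 50 mg the threshold is 0.80 × 700 = 560 mg; 11 doses (550 mg) fail and 12 doses (600 mg) pass. The definitions differ on missed doses but agree on the first two rows. Under either one, the number of Cycle 1 reductions in the named set is 0 of 3 by construction.

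**2. The plan's own enrolment figures.** Protocol 3.1 states: "The enrollment of approximately 76 advanced cancer patients is anticipated in this study in order to have 8 PK-evaluable patients". That number applies to four groups (A1, A2, B, C), and Group D adds 6. The evaluable target is 4 × 8 + 6 = 38, which matches Protocol 9.2 and SAP 4.1. The planning ratio is 76 / 38 = 2.0 enrolled per evaluable patient, an implied non-evaluable share of 1 − 38/76 = 50% from all causes.

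**3. Applied to stage 1 (assumption: the study-wide ratio holds there).**

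- If 50 mg is kept: 3 × 2.0 = 6 enrolled for 3 evaluable, so 3 are outside the named set.
- If the dose changes, Group C needs 3 + 8 evaluable patients and the study 38 + 3 = 41. Then 76 / 41 = 1.85; 3 × 76/41 = 5.56 enrolled and 2.56 outside (46%).

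**4. Range.** The documents give no non-evaluable share for Group C. Let d be that share for any reason, with patients enrolled until 3 are evaluable. Expected enrolment is 3 / (1 − d), and the chance that at least one patient is left out is 1 − (1 − d)³.

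| Assumed d | Expected enrolled | Chance at least one is left out |
|---|---|---|
| 10% | 3.3 | 27.1% |
| 20% | 3.75 | 48.8% |
| 30% | 4.3 | 65.7% |
| 40% | 5.0 | 78.4% |
| 50% (implied by 76 and 38) | 6.0 | 87.5% |

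These are not toxicity rates, and the patients left out may include some who were never dosed. Step 1 does not depend on them.

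**5. Whether other wording repairs the rule.** The phrase about the first 3 subjects could mean the first 3 enrolled. Once one patient is replaced, that set differs from the 3 PK-evaluable patients, but it still names 3 people and not everyone dosed at 50 mg.

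**The case against.** The strongest reply is that the documents, read as a whole, do not confine the safety review to 3 patients.

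- Protocol 9.4 and 9.6 provide ongoing sponsor review of individual and summary safety data.
- SAP 3.4.3 and 5.5 put safety summaries on all dosed patients. SAP 5 splits Group C by dose level, so C1 safety would by default cover everyone dosed at 50 mg.
- SAP 5.4.2.1 already summarises discontinuations, interruptions and reductions due to adverse events.
- Under Protocol 5.5, a step from 50 to 25 mg should be discussed with the sponsor, who also makes the stage-2 decision.
- SAP 6 uses 3 PK-evaluable patients as a trigger and does not restrict the safety population. The decision sentence can likewise be read as a milestone.
- Table 6 is recommended guidance, and toxicity that needs no dose change stays visible in the 3 patients.
- At a new dose, the first 3 patients are treated singly with a gap of a week or more.

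All of this stands, and it limits the practical harm: the sponsor would probably know of the replaced patients. But none of these provisions is tied to the stage-2 decision or changes the sentence that states its basis, and SAP 6 leaves open whose safety data are used. Staggered dosing protects patients after the decision; it does not inform it. If the intention is already to use all dosed patients, the correction only records it.

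**Conclusion.** The concern holds. As written, the tolerability basis for the stage-2 Group C dose excludes by definition patients whose 50 mg dose was reduced in Cycle 1 or who stopped before Cycle 2 Day 1. That follows from the definitions alone and needs no assumed rate.

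The number of patients affected is uncertain. About 3 of 6 stage-1 enrolees would fall outside the set if the study-wide, all-cause planning ratio applied. The share caused by toxicity is unknown, and nothing here shows that the dose decision would change or that data would be ignored. The defect is one of written decision basis: worth correcting because the rule governs a possible dose increase in hepatically impaired patients, and modest in practical effect because of the surrounding safety review.

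**What to change.** - **Protocol 3.1 and SAP 2.2, decision sentence:** split the basis. PK comes from the 3 PK-evaluable patients. Tolerability comes from all Group C stage-1 patients given at least one 50 mg dose, including any who were replaced.
- **Same sections, phrase on the first 3 subjects:** align it with that basis.
- **Same sections, starting dose:** say that all stage-1 Group C patients start at 50 mg, since replacements do too.
- **SAP 6:** state that the interim safety analysis covers all dosed C1 patients and shows Cycle 1 interruptions, reductions and discontinuations with reasons. Showing Cycle 1 Day 1 PK for replaced patients is optional.

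The cost is wording only. No extra patients, visits or data are needed: adverse events and dosing of replaced patients are already collected, and SAP 5.4.2.1 already plans the summaries. The sample size does not change. The one downside is that the tolerability picture may look less favourable.
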